7.1.3 Treatment exposure and compliance

Compliance with the study treatments will be assessed by the investigator and/or study personnel at each visit using pill counts and information provided by the patient or caregiver. This information should be captured in the source document at each visit for both drugs (everolimus and exemestane).

[figure not shown]
To accurately record the administration of study treatments, the following information must be recorded on the DAR CRF throughout the study:

- Planned dose administration
- Actual total dose administered
- Regimen
- Start/End date of drug administration
- Dose change or delay and reason for modification.

7.1.4 Discontinuation of the study drugs

Study discontinuation refers to a patient's withdrawal from everolimus. The reason for discontinuation from treatment must be recorded on the End of treatment CRF.

Everolimus will be discontinued for any of the following reasons:

- Disease progression
- Consent withdrawal
- Unacceptable adverse events
- Everolimus dose interruption of > 4 weeks
- Intercurrent illness that prevent further administration of everolimus treatment
- Need for any other types of anticancer therapy, except for palliative radiotherapy for bone lesions
- General or specific changes in the patient's condition which render the patient unacceptable for further everolimus treatment at the discretion of the investigator
- Death.

If a patient has discontinued both study treatments due to an unacceptable adverse drug reaction or an abnormal laboratory value, she should not have withdrawal of consent recorded as the reason for discontinuation. Instead, the reason for discontinuation must be recorded as due to adverse drug reaction or an abnormal laboratory value.

If everolimus or exemestane is permanently discontinued, the patient will be considered to have completed study treatment. All patients must have safety evaluations for 30 days (\pm 2 days) after the last dose of everolimus.

Patients who discontinue everolimus should be scheduled for an End of Treatment Visit, as soon as possible, after discontinuing everolimus, at which time all of the assessments listed for the End of Treatment Visit will be performed. The date and reason for stopping the study everolimus treatment should be recorded on the CRF.

Once the last dose of everolimus is taken, no further AEs/SAEs will be collected on this protocol beyond the 30 day follow-up safety interval.

[figure not shown]
7.1.5 End of the study

In each participating country, the study will end when everolimus is locally reimbursed or commercialized for this indication or when all patients have been discontinued from investigational treatment due to disease progression, unacceptable toxicity, death, consent withdrawal or any other reason.

Patients will be followed up for safety purposes for 30 days (\pm 2 days) after the last dose of study drug.

At the end of the study, the progression status of all participating patients will be updated and recorded in the CRF.

In those countries in which patients will be transitioned to locally reimbursed or commercialized drug supplies, Novartis will have a local transition plan in order to ensure that all on-going patients will still have access to the study medication without any delay in their treatment.

7.2 Safety and tolerability assessments

Safety and tolerability will be monitored by assessing all adverse events, including serious adverse events, the regular monitoring of hematology, blood chemistry, lipid profile, hepatitis B and C markers, vital signs, ECOG performance status and physical examination. Adverse events will be evaluated continuously throughout the study period. The other assessments should be performed based on the scheduled day of assessment (Refer to [Table 7-1](#)).

Toxicity will be assessed using the NCI-CTCAE Common Terminology Criteria for Adverse Events, version 4.03 (CTCAEv4.03). AE/SAE collection and reporting is detailed in [Section 8](#).

7.2.1 Physical examination, height and weight

Physical examination must comprise a total body examination (general appearance, skin, neck, including thyroid, eyes, ears, nose, throat, lungs, heart, abdomen, back, lymph nodes and extremities).

Physical examination will be performed at screening, on treatment Day 1 (prior to administration of the study drug, unless physical examination in screening was done less than 7 days before Day 1), as well as at Week 4, Week 10, Week 20, Week 30, Week 40, and Week 50 or End of treatment visit.

Information for all physical examinations must be included in the source documentation at the study site. Significant findings that are present prior to the start of study drug must be documented on the Medical History / Current medical Conditions CRF. Significant findings made after the start of study drug, which meet the definition of an adverse event, must be recorded on the Adverse Event CRF.

Height and weight will be measured at the screening visit.

7.2.2 Vital signs

Vital signs will be recorded on the appropriate CRF pages at each visit. Heart rate and blood pressure will be measured according to normal medical practice.

The particular clinical findings seen before taking study drug must be documented in the Relevant Medical History CRF. The findings that are compatible with adverse events after taking study drug must be documented in the Adverse Event CRF.

7.2.3 Laboratory evaluations

Laboratory evaluations should be performed locally at every protocol required visit ([Table 7-1](#)) or as frequently as clinically indicated. The patient should be in a fasting state for 12 hours at the time of blood sampling.

All scheduled laboratory evaluations must be obtained according to the specified visit window in [Table 7.1](#), whether or not study treatment is administered. Screening examinations performed ≤ 7 days of the first dose of study treatment do not need to be repeated on Day 1.

Laboratory values will be recorded in the patient's source documents and must not be documented in the CRF. However, any particular clinically significant findings seen before taking study drugs must be documented in the Relevant Medical History/Current Medical Conditions CRF.

Abnormal laboratory parameters that are considered clinically significant, induce clinical signs or symptoms, require concomitant therapy (e.g. hematologic abnormality that requires transfusion or hematological stem cell support), or require changes in study treatment, or require changes in study drug(s) constitute adverse events in their own right and must be recorded on the Adverse Events CRF.

Whenever possible, a diagnosis, rather than a symptom should be provided (e.g. anemia instead of low hemoglobin). Laboratory abnormalities that meet the criteria for Adverse Events should be followed until they have returned to normal or an adequate explanation of the abnormality is found. When an abnormal laboratory or test result corresponds to a sign/symptom of an already reported adverse event, it is not necessary to separately record the lab/test result as an additional event.

Laboratory abnormalities, that do not meet the definition of an adverse event, should not be reported as adverse events. A Grade 3 or 4 AE (severe) as per CTCAE does not automatically indicate a SAE unless it meets the definition of serious as defined below and/or as per investigator's discretion. A dose hold or medication for the lab abnormality may be required by the protocol and is still, by definition, an adverse event.

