3.1.1 Primary endpoints

The primary endpoints are safety and tolerability evaluations, assessed according to the Common Terminology Criteria (CTCAE), version 4.03. This includes the incidence of adverse events (AEs) by grade, incidence of serious adverse events (SAEs), changes from baseline in vital signs, as well as changes from baseline in laboratory results (hematology, blood chemistry, lipid profile, viral markers) qualifying as AEs.

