Enrolment in the study will be confirmed by completing the Enrolment form on the electronic case report form (eCRF). Information collected for screening failures include date of informed consent, inclusion/exclusion criteria, and serious adverse events (SAE) where relevant.

[figure not shown]
Treatment phase

Patients will start study treatment on Day 1 with everolimus 10 mg daily p.o. (either 2 x 5 mg or 1 x 10 mg tablets) in combination with exemestane 25 mg daily p.o. (25 mg tablets). Dose adjustment (reduction or interruption) will be allowed according to safety findings and dose adjustment guidelines. Study treatment will continue until disease progression, unacceptable toxicity, death, consent withdrawal or any other reason. Further treatment after progression will be at the investigator's discretion.

During the study, visits will be performed at Screening, Baseline/Treatment Day 1 (Treatment start), Week 4 (\pm 1 week), Week 10 (\pm 2 weeks), and then every 10-weekly (\pm 2 weeks) till end of treatment.

Tumor evaluations through CT scan/MRI will be performed for Screening, at Week 10, and 10 weekly thereafter. All radiological evaluations and laboratory assessments will be performed locally, at the center level. Patients will be followed up for safety for 30 days (\pm 2 days) after the last dose of everolimus. AEs/SAEs with a suspected causality to the study drug must be reported beyond this 30 days safety interval.

Figure 4-1 Study design

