7.1 Study flow and visits schedule

[Table 7-1](#) lists all study assessments by visit. All data obtained from these assessments must be supported in the patient's source documentation. All assessments will be captured in the CRF, with the only exception of safety laboratory tests and ECG, which will remain only in the patient's source documents.

Tests, procedures and visits should occur on schedule as far as possible.

[figure not shown]
[figure not shown]
[figure not shown]

Table 7-1 Schedule of assessments

[figure not shown]
	Screening Day -21 to -1	Baseline Day 1	Week 4 ± 1 week	Week 10 ± 2 weeks	Week 20 ± 2 weeks	Week 30 ± 2 weeks	Week 40 ± 2 weeks	Week 50 ± 2 weeks/ EOT	Following visits (each 10 ± 2 weeks)	EOT	Follow-up EOT + 30 days (± 2 days)
Visit N°	1	2	3	4	5	6	7	8	N	EOT	F-up
Informed consent	X										
Demographics	X										
Eligibility criteria	X	X									
Medical history, current medical conditions	X										
Diagnosis and extent of breast cancer	X										
Prior antineoplastic therapies	X										
Height, weight	X										
Physical examination	X	X	X	X	X	X	X	X	X	X	
Vital signs, ECOG status	X	X	X	X	X	X	X	X	X	X	
Prior medications	X										
Concomitant medications	X	X	X	X	X	X	X	X	X	X	X
Adverse events	X	X	X	X	X	X	X	X	X	X	X
Study drugs dispensation		X	X	X	X	X	X	X	X		
CT scan/MRI chest, abdomen,	X			X	X	X	X	X	X	X	

	Screening Day -21 to -1	Baseline Day 1	Week 4 ± 1 week	Week 10 ± 2 weeks	Week 20 ± 2 weeks	Week 30 ± 2 weeks	Week 40 ± 2 weeks	Week 50 ± 2 weeks/ EOT	Following visits (each 10 ± 2 weeks)	EOT	Follow-up EOT + 30 days (± 2 days)
Visit N°	1	2	3	4	5	6	7	8	N	EOT	F-up
pelvis (1)											
Brain CT scan or MRI (2)	X	As clinically indicated									
Bone scan/ X-ray (3)	X	If bone metastases are present at baseline, a bone scan or skeletal survey is required every 10 weeks. If bone metastases are not identified at baseline, bone scans will be performed as clinically indicated									
Bone CT/MRI (3)	X	If bone metastases are present at baseline, a bone scan or skeletal survey is required every 10 weeks. If bone metastases are not identified at baseline, bone CT/MRI will be performed only to confirm potential findings identified by bone scans/X-rays.									
Hematology, chemistry, lipid profile (5)	X	X	X	X	X	X	X	X	X	X	
Hepatitis B viral load and markers	X	Monitor approximately every 3-6 weeks when required.									
Hepatitis C viral load and markers	X	Monitor approximately every 6 weeks when required.									

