7.1.1 Screening period

The baseline visit/Treatment Day 1 will occur no later than 21 days after the screening visit. All assessments requested at the screening visit should be completed before Treatment Day 1.

The following assessments and procedures will be performed at the screening visit or requested at the screening visit to be completed within the screening period:

- Obtain patient's written informed consent form prior to any study-specific assessment
- General demographics including age and gender
- Medical history/current medical conditions (including prior concomitant medications within the last 4 weeks prior to Day 1)
- History and current disease status (including staging, diagnosis information, previous anticancer treatments and sites of disease). The following information must be collected for all previous anticancer therapies: date start, date end, setting (neoadjuvant, adjuvant, metastatic), best response, reason for treatment discontinuation.
- Physical examination, height and weight
- Vital signs including blood pressure and heart rate
- ECOG performance status
- Hepatitis B viral load and markers, hepatitis C viral load (see [Section 6.3.3.1](#) and [Section 6.3.3.2](#)).

The other safety laboratory assessments, including hematology, biochemistry, serum lipid profile, coagulation and urinalysis should be performed locally at the investigator's discretion and are not captured on the CRF. However, laboratory results that are out of range and clinically significant should be captured on the medical history/current medical conditions CRF.

[figure not shown]
The following radiological tumor assessments should be performed within the 21-day screening period prior to the start of study treatment:

- CT scan/MRI for chest, abdomen, and pelvis. CT scan/MRI with contrast media should be used except for patients who are allergic/sensitive to the radiographic contrast media.
- Brain: CT or MRI if CNS metastases are present
- Bone Scan and CT or X-ray to confirm existing bone lesions (according to local practice), unless performed within 6 weeks prior to the Baseline visit/Treatment Day 1.

Patients eligible to the study with positive HBV-DNA or HBsAg at screening must initiate prophylaxis with appropriate antiviral medication at least one week prior to treatment start (Treatment Day 1).

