7.2.3.5 Hepatitis B viral load and markers, hepatitis C viral load

HBV-DNA, HBsAg, HBsAb, HBcAb and HCV-RNA will be measured at screening. Significant findings must be recorded as Relevant Medical History / Current Medical Conditions.

[figure not shown]
These assessments will be repeated every 3-6 weeks during the treatment period when required. Results will be recorded in the CRF. Hepatitis reactivation or flare will be managed according to guidelines presented in [Section 6.3.3](#), and will be recorded on the Adverse Events CRF.

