9.2 Site monitoring

Before study initiation, Novartis personnel (or designated CRO) will review the protocol and CRFs with the investigators and their staff at a site initiation visit. During the study, the field monitor will visit the site regularly to check the completeness of patient records, the accuracy of entries on the eCRFs, the adherence to the protocol and to Good Clinical Practice, the progress of enrolment, and to ensure that study drug is being stored, dispensed, and accounted for according to specifications. Key study personnel must be available to assist the field monitor during these visits.

The investigator must maintain source documents for each patient in the study, consisting of case and visit notes (hospital or clinic medical records) containing demographic and medical information, laboratory data, electrocardiograms, and the results of any other tests or assessments. All information on eCRFs must be traceable to these source documents in the patient's file. The investigator must also keep the original informed consent form signed by the patient (a signed copy is given to the patient).

The investigator must give the monitor access to all relevant source documents to confirm their consistency with the eCRF entries. Novartis monitoring standards require full verification for the presence of informed consent, adherence to the inclusion/exclusion criteria, and documentation of SAEs. Additional checks of the consistency of the source data with the eCRFs are performed according to the study-specific monitoring plan.

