9.4 Database management and quality control

Data recorded on the eCRFs will be reviewed by a designated CRO staff for completeness and accuracy following their own internal standard operating procedures that have been reviewed and approved by Novartis.

Site personnel will be instructed to make any required corrections or additions. Obvious errors are corrected by CRO Data Management staff. Queries are sent to the investigational site using an electronic data query system. The designated investigator site staff is required to respond to the query and make any necessary changes to the data within a reasonable timeframe. If the electronic query system is not used, a paper Data Query Form will be faxed to the site. Site personnel will complete and sign the faxed copy. This copy will then be faxed back to the CRO Data Management staff that will make the correction to the database. The signed copy of the Data Query Form is kept at the investigator site.

Concomitant medications entered into the database will be coded using the WHO Drug Reference List, which employs the Anatomical Therapeutic Chemical classification system. Medical history/current medical conditions and adverse events will be coded using the Medical dictionary for regulatory activities (MedDRA) terminology.

Samples and/or data may be processed centrally and the results will be sent electronically to Novartis (or a designated CRO).

At the conclusion of the study, the occurrence of any emergency code breaks will be determined after return of all code break reports and unused drug supplies to Novartis (or designated CRO). The occurrence of any protocol violations will be determined. After these actions have been completed and the database has been declared to be complete and accurate, the database will be locked and made available for data analysis. Any changes to the database after that time can only be made by joint written agreement between the Global Head of Biostatistics and Statistical Reporting and the Global Therapeutic Area Head.

[figure not shown]
10 Statistical methods and data analysis

The study is designed as an open-label, single-arm, phase IIIB trial to assess the safety, tolerability and efficacy of everolimus plus exemestane in postmenopausal women with hormone receptor positive breast cancer progressing following prior therapy with non-steroidal aromatase inhibitors.

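### Safety laboratory values are barred from the CRF yet fill 22 SAP outputs; the late adverse-event rules, the AE listings and the grouped special-interest table also need aligning

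*Protocol*

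**What the plan says.** **Laboratory data.** Protocol 7.1 captures every assessment in the CRF "with the only exception of safety laboratory tests and ECG, which will remain only in the" patient's source documents. Section 7.1.1 leaves screening haematology, biochemistry, lipids, coagulation and urinalysis to the investigator's "discretion and are not captured on the CRF". Section 7.2.3 is unqualified: values belong in "source documents and must not be documented in the CRF". Section 7.2.3.5, however, says of hepatitis B and C results: "Results will be recorded in the CRF". The SAP plans haematology Tables 10.2.1 to 10.2.7, biochemistry Tables 10.3.1 to 10.3.7, lipid Table 10.4, and Listings 18.1.1 to 18.5 of individual results.

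**Late events.** Protocol 6.5 and 7.1.4 say that no AEs or SAEs are collected beyond 30 days after the last everolimus dose. The protocol summary, 4.1 and 7.1.2 say that AEs and SAEs suspected to be drug-related must be reported beyond that point. Section 8.2.2 has late SAEs reported only if causality is suspected. Section 10.5 promises a by-patient listing of all AEs noted during the study, and says that AEs starting more than 30 days after discontinuation are listed but not tabulated.

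**Special-interest events.** Protocol 8.1.3 names 11 terms associated with mTOR inhibition. SAP Table 6.13 is the grouped summary of them.

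**The concern.** Safety is the primary objective. If the CRF follows the protocol, programmers hold shells for change from baseline, CTC-grade shifts and normal-range shifts with no described source, and a database-level check of whether laboratory abnormalities were reported as AEs is not possible. If the eCRF does capture the values, three protocol sections tell sites not to enter what the analysis needs.

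On late events, sites hold instructions that do not agree as written, and events outside the treatment-emergent window have no visible planned output. The grouped special-interest summary would not match the protocol's own list.

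**Working it through.** No sample-size or power figure is involved. The check is a count of shells and a comparison of passages.

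1. **Laboratory outputs.** Tables: 7 (10.2.x) + 7 (10.3.x) + 1 (10.4) = 15. Listings 18.1.1, 18.1.2, 18.2.1, 18.2.2, 18.3, 18.4, 18.5, 18.6 and 18.7 make 9. The two hepatitis listings (18.6, 18.7) have a CRF source under 7.2.3.5, so 9 − 2 = 7. Total: 15 + 7 = 22.

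2. **Distinct displays.** Eight tables repeat another for Asian or non-Asian patients (10.2.3, 10.2.4, 10.2.6, 10.2.7, and 10.3.3, 10.3.4, 10.3.6, 10.3.7). Listings 18.1.2 and 18.2.2 are out-of-range filters of 18.1.1 and 18.2.1. 22 − 8 − 2 = 12.

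3. **Another data route?** Section 4.1: "All radiological evaluations and laboratory assessments will be performed locally, at the center level". Section 9.4 has only a general line: "Samples and/or data may be processed centrally and the results will be sent electronically to Novartis" or a CRO. No transfer of local laboratory values is described.

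4. **Could the eCRF hold the values anyway?** The laboratory listing shells carry an Assessment Not Done column. Listings 18.3 to 18.5 have a laboratory number, 18.3 has a fasting flag, and 18.1.1 to 18.2.2 have normal limits. These look like data-entry fields, so capture is plausible but not shown.

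5. **Effect on the primary endpoint.** Section 3.1.1 covers only "changes from baseline in laboratory results (hematology, blood chemistry, lipid profile, viral markers) qualifying as AEs". Those reach the AE CRF by a separate route (7.2.3, 8.1.2), so AE, SAE and vital-sign outputs do not depend on the values.

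6. **ECG.** Section 7.1 also keeps ECGs out of the CRF, yet Listing 17 reports them. Its content columns are clinically significant abnormalities, and 7.2.3.6 sends notable findings to the Medical History or Adverse Events CRF, so it can be partly filled.

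7. **Late events, side by side.** Protocol 6.5 and 7.1.4 collect nothing after 30 days. The summary, 4.1 and 7.1.2 make reporting of suspected events compulsory after 30 days. Section 8.1.1, which monitors for at least 30 days, and 8.2.2, which covers SAEs only, are compatible with the second group.

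8. **Listings against 10.5.** Listings 14.1 to 14.3 are all titled treatment-emergent. The SAP defines this as starting on or after first dose and within 30 days of discontinuation (Table 6.1 footnote). Section 8.1.1 records AEs from informed consent, except in screening failures. Two groups therefore fall outside all 3 listings: AEs between consent and first dose, and AEs starting more than 30 days after discontinuation.

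9. **Special-interest terms.** Protocol 8.1.3 has 11 terms. Below its any-event row, Table 6.13 has 10. Wound healing complications is missing, and cardiac failure has become congestive cardiac failure. Tables in this layout: 6.13 and 6.13A to E (6) + S2.6.13 and S2.6.13A to C (4) = 10.

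**The case against.** A reader might infer that the primary safety analysis lacks data. The documents do not support that. The laboratory endpoint is limited to changes that qualify as AEs, the shells hint that values may be captured, and source checks remain: "Additional checks of the consistency of the source data with the eCRFs are performed according to the study-specific monitoring plan". The count of 22 also overstates the variety of displays affected.

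A reader might infer that late drug-related SAEs would go unreported. Collection within the study and reporting to the sponsor's safety department can be separate channels, and 8.2.2 gives a route for late suspected SAEs. That reading may reconcile the passages for SAEs. It does not do so for non-serious suspected AEs, which the summary, 4.1 and 7.1.2 also cover but for which no such route is given. Nor does it explain how 10.5 can list late AEs that are not collected.

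It would also be too strong to say that no listing of late AEs exists. Listing 22 and the Table 9 area are not visible in the SAP. Listing 22 falls between the skeletal survey and broncho-alveolar lavage listings, so it is unlikely to hold AEs, but the statement must be limited to visible shells.

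Finally, wound-healing and non-congestive cardiac events are not lost from reporting. Tables 6.11, 6.12, 6.12.1 and 6.12.2 are built by system organ class and preferred term without fixed rows, Table 6.1 counts patients with any special-interest event, and the general treatment-emergent tables also apply. This objection stands and makes the third item minor.

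**Conclusion.** The contradictions are real and should be fixed before programming.

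- **Laboratory data (main item).** 22 planned outputs, about 12 distinct displays, conflict with Protocol 7.1, 7.1.1 and 7.2.3. Which document is wrong cannot be decided without the eCRF. The contradiction is certain; a loss of laboratory data is only one of two possibilities. Section 7.2.3 also needs aligning with 7.2.3.5, which differs from it without being written as an exception.
- **Late events.** Two protocol sections must be reconciled with three other places. The difficulty is clearest for non-serious AEs. None of the 3 visible AE listings covers the non-treatment-emergent events that 10.5 says will be listed.
- **Special-interest table (minor).** One of 11 terms has no row and one is narrowed, in one layout used for 10 tables.

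This rests on the current protocol text and the visible SAP shells.

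**What to change.** 1. Check the eCRF. If it captures the laboratory values, correct 7.1, 7.1.1 and 7.2.3 to say so, and align 7.2.3 with 7.2.3.5; this is a text change only. If it does not, delete Tables 10.2.1 to 10.4 and Listings 18.1.1 to 18.5, limit Listing 17 to ECG findings recorded in the CRF, and state in 10.5 and the SAP that laboratory safety is reported through AEs only. That adds no site work but gives up database-level shifts; monitors' access to source remains.

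2. Reconcile 6.5 and 7.1.4 with the summary, 4.1 and 7.1.2, separately for SAEs and non-serious AEs, and check 8.1.1, 8.2.2 and 10.5 against the result. The choice of rule is the sponsor's.

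3. Add one SAP listing of all non-treatment-emergent AEs, covering those between consent and first dose and those starting more than 30 days after discontinuation. Cost: one shell.

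4. Add a wound healing complications row to Table 6.13 and use the 8.1.3 term for cardiac failure, carrying both through the nine other tables in that layout. Cost: one row and one label in 10 shells.
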